3. STUDY OBJECTIVES AND ENDPOINTS

3.1. Study Objectives

Primary Objective

To evaluate the clinical efficacy, as assessed by time to recovery, of different investigational therapeutics as compared to the control arm.

Secondary Objectives

The key secondary objective is to evaluate the clinical efficacy of different investigational therapeutics relative to the control arm in adults hospitalized with COVID-19 according to clinical status (8-point ordinal clinical scale) at Day 15.

The other secondary objectives are to:

1. Evaluate clinical efficacy of different investigational therapeutics as compared to the control arm as assessed by:
 - Clinical Severity
 - 8-Point Clinical Status Ordinal scale:
 - Time to an improvement of one category and two categories from Day 1 (baseline) on the clinical status 8-point ordinal scale.
 - Subject clinical status using 8-point ordinal scale at Days 3, 5, 8, 11, 15, 22, and 29.
 - Mean change in the clinical status 8-point ordinal scale from Day 1 to Days 3, 5, 8, 11, 15, and 29.
 - National Early Warning Score (NEWS):
 - Time to discharge or to a NEWS of ≤ 2 and maintained for 24 hours, whichever occurs first.
 - Change from Day 1 to Days 3, 5, 8, 11, 15, and 29 in NEWS.
 - Oxygenation:
 - Oxygenation use up to Day 29.
 - Incidence and duration of new oxygen use through Day 29.
 - Non-invasive ventilation/high flow oxygen:
 - Non-invasive ventilation/high flow oxygen use up to Day 29.
 - Incidence and duration of new non-invasive ventilation or high flow oxygen use through Day 29.
 - Invasive Mechanical Ventilation / extracorporeal membrane oxygenation (ECMO):
 - Ventilator/ECMO use up to Day 29.
 - Incidence and duration of new mechanical ventilation or ECMO use through Day 29.

- Hospitalization
 - Duration of hospitalization (in days) through Day 29.
 - Mortality
 - 14-day mortality.
 - 28-day mortality.
2. Evaluate the safety of the intervention through 28 days of follow-up as compared to the control arm as assessed by:
- Cumulative incidence of SAEs through Day 29
 - Cumulative incidence of Grade 3 and 4 clinical and/or laboratory AEs through Day 29.
 - Discontinuation or temporary suspension of study product administrations (for any reason).

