3.3.6. Days of Non-invasive ventilation/high-flow oxygen

Non-invasive ventilation/high flow-oxygen days will be defined as the number of days where the clinical status score is equal to 6. After discharge, the Post-Discharge Supplemental Oxygen CRF questions regarding days of non-invasive ventilation or high-flow oxygen will be used. The total number of days will be the sum of all reported days, regardless of whether the days occur consecutively or in disjoint intervals. See Section 6.5 for the plan for handling subjects who do not have data through Day 29 or die prior to Day 29.

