3.3.7. Days of Invasive Mechanical Ventilation/ECMO

Invasive Mechanical Ventilator / ECMO days will be defined as the number of days where the clinical status score is equal to 7. After discharge, the Post-Discharge Supplemental Oxygen CRF questions regarding days of ECMO or invasive ventilation will be used. The total number of days will be the sum of all reported days, regardless of whether the days occur consecutively or in disjoint intervals. See Section 6.5 for the plan for handling subjects who do not have data through Day 29 or die prior to Day 29.

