3.3.8. Days of Oxygen

Oxygen days will be defined as the number of days where the clinical status score is equal to 5, 6, or 7. After discharge, the Post-Discharge Supplemental Oxygen CRF question regarding days of oxygenation (including ECMO, invasive ventilation, non-invasive ventilation, high-flow oxygen devices, and all other oxygen delivery devices) will be used. The total number of days will be the sum of all reported days, regardless of whether the days occur consecutively or in disjoint intervals. See Section 6.5 for the plan for handling subjects who do not have data through Day 29 or die prior to Day 29.

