Oxygenation, Non-invasive ventilation/high flow oxygen, Invasive Mechanical Ventilation / extracorporeal membrane oxygenation (ECMO), hospitalization and mortality will be assessed using results of the 8-point ordinal scale and post discharge eCRF questions.

Safety will be assessed by the following:

- Cumulative incidence of serious adverse events (SAEs) through 28 days of follow-up.
- Cumulative incidence of Grade 3 and 4 AEs.
- Discontinuation or temporary suspension of study product administration (for any reason)

- Changes in white cell count, absolute neutrophil count, hemoglobin, platelets, creatinine, glucose, total bilirubin, ALT, AST, and INR, d-dimer, C-reactive protein over time.

Clinical labs will be drawn on Days 1, 3, 5, 8, 11 and on Day 15 and 29 if the subject is able to return to the clinic or is still hospitalized.

Virologic efficacy is an exploratory endpoint and will be assessed by the following:

- Qualitative and quantitative PCR for SARS-CoV-2 in OP swab on Days 1; 3, 5, 8, 11 (while hospitalized); and Day 15 and 29 (if able to return to clinic or still hospitalized).
- Qualitative and quantitative PCR for SARS-CoV-2 in blood on Days 1; 3, 5, 8, 11 (while hospitalized).

To assess the impact of baricitinib on serum cytokine levels, blood samples will be assessed using a multiplex assay that is less sensitive to variability in sample integrity due to sample processing limitations during the pandemic. Cytokines to be tested may include (but not be limited to) IL-2, IL-19, IL-4, IL-10, IL-8, G-CSF, GM-CSF, MCP-1, MIP1 α , IL-7, IL-13, IL-31, IL-15, IL-6, IFN α , IFN γ and TNF α . The list of cytokines tested is subject to change as new information about the pro-inflammatory state of COVID-19 is known. Given the challenges of obtaining samples and evolving knowledge about COVID-19, these will be considered exploratory endpoints. The description of the final methodology utilized, and the assay performance characteristics will be included in the final study report.

The schedule of study procedures is provided in Section 1.2 of Appendix B of the study protocol.

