8.2.4. Incidence of New Oxygen use

The incidence and duration of new oxygen use will be analyzed by treatment arm. This will only include subjects in category 4 at randomization. New use will be identified by a post-enrollment score of at least 5; the number of subjects reporting new use and the incidence rate (and CI) will be reported.

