8.2.6. Incidence of New Non-Invasive Ventilation/High-Flow Oxygen

The incidence and duration of new Non-Invasive Ventilation/High-Flow Oxygen use will be analyzed by treatment arm. This will only include subjects in category 4 or 5 at randomization. New use will be identified by a post-enrollment score of 6. The number of subjects reporting new use and the incidence rate (and CI) will be reported.

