8.2.8. Incidence of New Invasive Mechanical Ventilation/ECMO

The incidence and duration of new Invasive Mechanical Ventilation/ECMO use will be analyzed by treatment arm. This will only include subjects in category 4, 5, or 6 at randomization. New use will be identified by a post-enrollment score of 7. The number of subjects reporting new use and the incidence rate (and CI) will be reported.

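### SAP 8.2.4, 8.2.6 and 8.2.8 identify new respiratory support by ordinal score alone, so support recorded only on the post-discharge CRF adds duration days but is not an incidence event

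*SAP*

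**What the plan says.** The three incidence rules each name one data source:

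- New oxygen (SAP 8.2.4, baseline category 4): "New use will be identified by a post-enrollment score of at least 5".
- New non-invasive ventilation or high-flow oxygen (SAP 8.2.6, baseline category 4 or 5): "New use will be identified by a post-enrollment score of 6".
- New invasive ventilation or ECMO (SAP 8.2.8, baseline category 4, 5 or 6): "New use will be identified by a post-enrollment score of 7".

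SAP 4.3 names two sources for this family of outcomes. Its sentence covers oxygenation and both ventilation types and ends "hospitalization and mortality will be assessed using results of the 8-point ordinal scale and post discharge eCRF questions".

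The duration definitions use both sources. For high-flow, SAP 3.3.6 has "After discharge, the Post-Discharge Supplemental Oxygen CRF questions regarding days of non-invasive ventilation or high-flow oxygen will be used". For ventilation, SAP 3.3.7 has "After discharge, the Post-Discharge Supplemental Oxygen CRF questions regarding days of ECMO or invasive ventilation will be used". For oxygen, SAP 3.3.8 counts days scored 5, 6 or 7 and then brings in "After discharge, the Post-Discharge Supplemental Oxygen CRF question regarding days of oxygenation".

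The objective in SAP 3.1 pairs incidence with duration and sets the same horizon for both, for example "Incidence and duration of new mechanical ventilation or ECMO use through Day 29".

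**The concern.** One objective covers incidence and duration over one window, but the two halves use different data. Scores 5, 6 and 7 all describe hospitalized patients. Under SAP 3.2 a patient at home on oxygen scores 2, and SAP 6.5 treats 2 as the highest value a non-hospitalized patient can have. Oxygen used only at home therefore cannot meet the 8.2.4 rule, although its days are added under 3.3.8.

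At stake is whether the reported incidence of new support matches its objective, and whether the arms are observed equally well. Capture by score is daily in hospital. After discharge it is limited to Days 15, 22 and 29, each describing the previous day (Protocol Appendix B, 8.1.2.2). An arm that discharges earlier spends more time under the sparser capture, and earlier recovery, which includes discharge, is the effect under test.

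**Working it through.** The plan states no incidence figure that depends on these rules, so there is nothing to reproduce. The check is to apply the written rules to constructed subjects, all in baseline category 4.

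**Inputs**

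- Incidence of new oxygen: any post-enrollment score of 5 or more (SAP 8.2.4). New ventilation: a score of 7 (SAP 8.2.8).
- Oxygen days: days scored 5, 6 or 7, plus post-discharge CRF days (SAP 3.3.8).
- Scores: every hospitalized day through Day 29, plus Days 15, 22 and 29 after discharge (Protocol Appendix B, 8.1.2.1 and 8.1.2.2).
- Readmission: data collection is left to the Manual of Procedures (Protocol Appendix B, 7.4), which is not among the documents.

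**Results** (days are observed days, before any imputation for death)

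| Subject | New oxygen (8.2.4) | New ventilation (8.2.8) | Oxygen days (3.3.8) |
|---|---|---|---|
| A. Home oxygen Days 10–17; visit scores 2, 2, 2 | No | No | 8 (all CRF) |
| B. Readmitted and ventilated; scores of 7 recorded on Days 13–16 | Yes | Yes | 4 (all scored) |
| C. Readmitted Days 16–19 with no scores taken; visit scores 2, 2, 2; CRF gives 4 oxygen days | No | No | 4 (all CRF) |
| D. Readmitted Days 20–24 on oxygen; Day 22 score 5 | Yes | No | 5 (1 scored, 4 CRF) |
| E. Dies after discharge, score 8, no oxygen recorded | Yes | No | 0 |

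A and C show the inconsistency: positive duration, no event. B and D show that support started after discharge is counted when a score records it. E is a side effect of the open-ended threshold: a score of 8 for death satisfies the new-oxygen rule with no oxygen recorded.

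**Is C realistic?** SAP 6.5 provides for subjects readmitted before Day 15 without a clinical score and imputes 7, but only for the key secondary outcome. The plan thus foresees unscored readmissions and gives the incidence endpoints no rule for them.

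**Knock-on in the tables.** The programming note to Table 42 limits the duration rows, among those not on oxygen at baseline, to subjects who reported new use. Tables 43 to 47 share the format. If new use means the score rule, the CRF days of A and C are lost from those rows as well.

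**Illustration of the level.** These rates are assumed and are not in the documents. Let *p* be the score-based incidence of new oxygen and *q* the proportion of the remaining subjects whose oxygen appears only on the CRF. Incidence with both sources is *p* + (1 − *p*)*q*.

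- *p* = 20%: *q* = 2%, 5%, 10% gives 21.6%, 24.0%, 28.0%.
- *p* = 40%: *q* = 2%, 5%, 10% gives 41.2%, 43.0%, 46.0%.

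These are shifts within an arm. The between-arm bias is only the difference between the two arms' shifts, and nothing in the documents allows it to be calculated.

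**The case against.** **A reader might infer that support begun after discharge is never an event, or that follow-up for incidence ends at discharge.** The documents do not support this. Daily scoring applies whenever the subject is hospitalized through Day 29 and is not restricted to the first stay, and there are three scheduled assessments after discharge. Subjects B and D are counted. If post-discharge high-flow and invasive ventilation are mostly given on readmission (an assumption), the gap matters less for 8.2.6 and 8.2.8 than for 8.2.4.

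**A reader might also put a number on the bias.** For example, assuming that 2–5% are readmitted and 20–40% of those are newly ventilated gives 0.02 × 0.20 = 0.4 to 0.05 × 0.40 = 2.0 percentage points missed. Those rates are not in the documents, the product treats every ventilated readmission as unscored, and it is a level in one arm rather than a difference between arms.

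**Home oxygen may be a narrow case.** Inpatient scoring takes the worst status of each day, so a category-4 patient who receives oxygen in hospital before going home on it should score 5 and be counted. That stands: only oxygen first used at home is missed. Excluding it could also be a deliberate choice of estimand, but the SAP does not say so, and 3.3.8 counts the same days.

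**The text is looser than a strict contradiction.** SAP 4.3 is a general statement of sources and does not say that every derived variable uses both. The Table 42 note could be read to include use reported on the CRF. Both points are fair. They leave the incidence rules open to two programmings, and the explicit sentences in 8.2.4, 8.2.6 and 8.2.8 name only the score.

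**Conclusion.** The point holds in limited form. Support recorded only on the post-discharge CRF contributes days under SAP 3.3.6 to 3.3.8 but is not new use under 8.2.4, 8.2.6 or 8.2.8. For oxygen first used at home, this follows from the rules alone. For unscored readmissions, it depends on how often scores are absent, which the Manual of Procedures would govern. The loss from the duration rows of Tables 42 to 47 assumes that reported new use there means the score rule.

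The likely direction favours the arm that discharges earlier, because more of its follow-up lies where scores are sparse. No size can be attached to this from the documents.

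These are additional secondary endpoints without multiplicity adjustment (SAP 6.8). The primary and key secondary analyses are not affected. The change should be made, but it does not threaten the trial's main conclusions.

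**What to change.** In SAP 8.2.4, 8.2.6 and 8.2.8, define new use as either of the following through Day 29:

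- a qualifying post-enrollment score: 5, 6 or 7 for oxygen (so that a score of 8 for death alone does not count), 6 for non-invasive ventilation or high-flow oxygen, and 7 for invasive ventilation or ECMO; or
- at least one day of the corresponding support on the Post-Discharge Supplemental Oxygen CRF.

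Use the same set of subjects for the new-use duration rows of Tables 42 to 47, and say so in the programming note.

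If an inpatient-only incidence is what the sponsor intends, the alternative is to state that and align SAP 3.1, 4.3 and the Table 42 note with it.

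The cost is SAP wording and one derivation line. The CRF data already feed the duration endpoints, so nothing new has to be collected.

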8.2.5. Days of Non-Invasive Ventilation/High-Flow Oxygen

Duration of non-invasive ventilation/high flow oxygen days will be summarized in a table using medians and quartiles by treatment arm. This will only include subjects in category 6 at randomization. Analyses will be performed in the ITT and As Treated populations. Bee swarm plots of non-invasive ventilation/high flow oxygen days by treatment arm will be generated, where subjects whose days are imputed to the maximum of 28 days due to death are grouped separately from subjects who do not die.

8.2.6. Incidence of New Non-Invasive Ventilation/High-Flow Oxygen

The incidence and duration of new Non-Invasive Ventilation/High-Flow Oxygen use will be analyzed by treatment arm. This will only include subjects in category 4 or 5 at randomization. New use will be identified by a post-enrollment score of 6. The number of subjects reporting new use and the incidence rate (and CI) will be reported.

8.2.7. Days of Invasive Mechanical Ventilation/ECMO

Duration of invasive Mechanical Ventilation/ECMO days will be summarized in a table using medians and quartiles by treatment arm. This will only include subjects in category 7 at randomization. Analyses will be performed in the ITT and As Treated populations. Bee swarm plots of invasive Mechanical Ventilation/ECMO days, and days hospitalized by treatment arm will be generated, where subjects whose days are imputed to the maximum of 28 days due to death are grouped separately from subjects who do not die.

8.2.8. Incidence of New Invasive Mechanical Ventilation/ECMO

The incidence and duration of new Invasive Mechanical Ventilation/ECMO use will be analyzed by treatment arm. This will only include subjects in category 4, 5, or 6 at randomization. New use will be identified by a post-enrollment score of 7. The number of subjects reporting new use and the incidence rate (and CI) will be reported.

8.2.9. Days of Hospitalization

Duration of hospitalization days will be summarized in a table using medians and quartiles by treatment arm. Incidence of readmittance will also be summarized ([Table 48](#)). Analyses will be performed in the ITT and As Treated population. Bee swarm plots of days hospitalized by treatment arm will be generated, where subjects whose days are imputed to the maximum of 28 days due to death are grouped separately from subjects who do not die.

8.3. Exploratory Efficacy Analyses

Analyses of exploratory outcome measures are not covered in this SAP.

9. SAFETY EVALUATION

9.1. Demographic and Other Baseline Characteristics

Summaries of age, sex, height, weight, BMI, ethnicity, and race will be presented by treatment group as well as geographic region, comorbidities, duration of symptoms prior to enrollment, and disease severity (Table 50 and Table 51). Ethnicity will be categorized as Hispanic or Latino, or not Hispanic and not Latino. In accordance with NIH reporting policy, subjects may self-designate as belonging to more than one race or may refuse to identify a race, the latter reflected in the CRF as “No” to each racial option.

Individual subject listings will be presented for all demographics and baseline characteristics (Listing 7).

9.1.1. Prior and Concurrent Medical Conditions

Focused medical history is obtained at the screening visit that includes the following:

- History of chronic medical conditions related to inclusion and exclusion criteria
- Review medications and therapies for this current illness.

Medical history is limited to the following conditions: asthma, cancer, cardiac valvular disease, chronic kidney disease, chronic liver disease, chronic oxygen requirement, chronic respiratory disease, coagulopathy, congestive heart failure, coronary artery disease, current nicotine consumption, diabetes I and II, hypertension, immune deficiency, obesity, and risk for deep vein thrombosis (DVT) or pulmonary embolism (PE). All current illnesses and past pre-existing medical conditions will be MedDRA® coded using MedDRA dictionary version 23.0 or higher. Summaries of subjects’ pre-existing medical conditions will be presented by treatment group (Table 52).

Individual subject listings will be presented for all medical conditions (Listing 8).

9.1.2. Prior and Concomitant Medications

Medication history (concomitant medications) includes a review of all current medications and medications taken within 7 days prior to enrollment through approximately Day 15 or early termination (if Day 15), whichever occurs first.

Summaries of medications that were started prior to dosing and continued at the time of dosing or started after dosing while on study will be presented by WHO Drug Level 1 and 2 Codes, disease severity, and treatment group (Table 53). Summaries of overall use of prohibited medications/therapies listed in Section 6.4 that were started prior to dosing and continued at the time of dosing or started after dosing while on study as well as use by select study days will also be generated (Table 54 and Table 55).

Individual subject listings will be presented for all concomitant medications (Listing 9).

9.2. Measurements of Treatment Compliance

Table 4 will provide summaries of key treatment compliance milestones/variables. In addition, the number of subjects with halted, slowed, or missed doses will be summarized by treatment arm (See Section 7).

Individual subject listings will be presented for all subjects who discontinued dosing (Listing 2). Individual subject listings will be presented for all subjects who missed, halted or slowed any doses (Listing 10).

9.3. Adverse Events

For the calculation of incidence of adverse events (i.e., on a per subject basis), each subject will only be counted once and any repetitions of adverse events within a subject will be ignored; the denominator will be the number of subjects in the Treated population. All adverse events reported will be included in the summaries and analyses.

An overall summary by treatment arm and disease severity of adverse events is presented that includes, but not limited to: subjects with at least one event, at least one related event, at least one SAE, at least one related SAE and at least one AE leading to early termination (Table 56 and Table 57).

Adverse events occurring in 5% of subjects (by MedDRA preferred term) in any treatment group will be presented (Table 58).

The proportion of subjects reporting at least one adverse event will be summarized by MedDRA system organ class and preferred term for each treatment arm, disease severity and overall. Denominators for percentages are the number of subjects in the Treated population.

The following summaries for adverse events will be presented by MedDRA system organ class, preferred term, disease severity and treatment group:

- Treatment-emergent renal adverse events by preferred term (Table 61);
- Treatment-emergent hepatic adverse events by preferred term (Table 62);
- Related adverse events by MedDRA system organ class and preferred term (Table 63);
- Subject listing of non-serious adverse events (Listing 11);
- Bar chart of non-serious related adverse events by severity and MedDRA system organ class (Figure 37);
- Bar chart of non-serious related adverse events by maximum severity and MedDRA system organ class (Figure 40);

9.4. Deaths, Serious Adverse Events and other Significant Adverse Events

Listings of death and other serious adverse events will be presented, including Subject ID, treatment group, Adverse Event Description, Number of Days Post Dose (Duration), Number of Days Post Dose the Event Became Serious, Reason Reported as an SAE, Severity, Relationship

to Treatment, Alternate Etiology if not Related, Action Taken with Study Treatment, Subject Discontinuation, Outcome, MedDRA SOC, and MedDRA PT (Listing 14 and Listing 16).

The number of subjects who die by Day 15 and Day 29 will be presented by treatment arm. The 14- and 28-day mortality rate, which will use Kaplan-Meier estimator, will be presented (Table 64).

Mortality through Day 15 and 29 will also be analyzed as a time to event endpoint (see Section 3.3). A table will present median time to event along with 95% confidence intervals overall for each treatment arm along with the hazard ratio estimate and log rank p-values (Table 66). Differences in time-to-event endpoints by treatment will be summarized with Kaplan-Meier curves (Figure 44). Analyses of mortality will be performed in the ITT and the Treated analysis populations. As a supplemental analysis, a Cox model will be fit with binary indicators for treatment group and disease severity as well as a treatment * disease severity interaction term. The model will be fit in the ITT and Treated analysis populations. The treatment group hazard ratios and CIs and the interaction term p-value will be reported. Finally, the results of the sensitivity time-to event analysis described in Section 6.4 will be presented in a table; the same summaries as in Table 66 will be provided. As requested by the DSMB, a restricted mean survival time analysis of mortality will be performed as an exploratory analysis. The restricted mean mortality time estimates will be provided for each treatment group and randomized disease severity stratum as well as the difference in restricted mean recovery time between treatment groups within each of the severity strata (Table 72).

Rates of Grade 3 and 4 AE occurrence will be compared between treatment arms using Barnard's exact test and presented. Rates of SAE occurrence will also be compared between treatment arms using Barnard's exact test and presented. Further, the composite endpoint of the occurrence of death, SAE, or Grade 3 or 4 AE described in Section 3.3 will be analyzed as a time to event outcome. A table will present median time to event along with 95% confidence intervals overall for each treatment arm along with the hazard ratio estimate and log rank p-values (Table 73). Differences in time-to-event endpoints by treatment will be summarized with Kaplan-Meier curves.

A summary of the infections reported on the AE CRF will be summarized by treatment group and disease severity (Table 74). The anatomical location(s) of the infection and causative pathogen(s) determined by culture will be summarized. Infections considered to be opportunistic, as identified by the sponsor, will also be included in the summaries.

